9.3.3 Assessment of the Outcome of Adverse Events

The Investigator will record the outcome of AEs and SAEs using the following criteria:

- **Recovered/resolved:** The subject has fully recovered from the event, with no residual effects observable.
- **Recovered/resolved with sequelae:** The subject has recovered from the event, but with residual sequelae effects observable.
- **Not recovered/resolved:** Effects of the event are still present.
- **Recovering/resolving:** The subject has improved but has not fully recovered from the event.
- **Fatal:** The death is related to the event.
- **Unknown:** The outcome of the event is unknown to the reporter (e.g., subject was lost to follow-up).

9.4 Reporting of Adverse Events

The Investigator is responsible for ensuring that all AEs and SAEs are recorded in the subject's medical record, AE eCRF, and/or SAE form, and reported to the Sponsor in accordance with protocol instructions. The AE eCRF can be used to report both AEs and SAEs. If necessary, e.g., in case of failure of the Electronic Data Capture (EDC) system or for logistical reasons, a paper AESI/SAE/Special Situation reporting form may be used instead.

9.4.1 Adverse Event Reporting Period

After signing of the Informed Consent all significant medical conditions including signs/symptoms of the underlying disease and known pre-existing medical conditions found during the screening period and up to initiation of dosing will be captured as medical history. Any event/condition, including those related to participation in the study or study procedures, those not related to underlying disease or pre-existing medical conditions already part of medical

history, and occurring before first dose of study treatment will be captured as a non-treatment emergent AE.

Any event/condition noted once the subject receives their dose of study drug will be captured as a treatment emergent AE. All AEs and SAEs regardless of attribution will be collected until at least 90 days following the last administration of study drug or the subject's EOS visit, whichever is later. At the last scheduled visit, the Investigator should instruct each subject to report to the Investigator any subsequent AEs/SAEs that the subject's personal physician believes could be related to prior study treatment.

SAEs unrelated to study treatment and non-serious AEs are to be followed until the last scheduled study visit (EOS visit), with the outcome at that point of time to be recorded in the eCRF. SAEs related to study treatment (Serious Adverse Drug Reactions) are to be followed until resolution or until they return to baseline, stabilize, or the subject is lost to follow-up. Resolution of AEs and SAEs (with dates) should be documented on the AE eCRF and SAE form (if applicable) and in the subject's medical record to facilitate source data verification. For some SAEs, the Sponsor or its designee may follow up by telephone, facsimile, electronic mail, and/or a monitoring visit to obtain additional case details deemed necessary to appropriately evaluate the SAE report (e.g., hospital discharge summary, consultant report, or autopsy report).

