9.2.1 Adverse Events

An AE is any untoward medical occurrence associated with the use of a drug in humans, whether considered drug related or not. Adverse events can include any unfavorable, noxious, unintended sign, symptom, or disease temporally associated with use of a study drug or other protocol-imposed intervention, regardless of attribution. Adverse events may be spontaneously reported

by the subject, discovered by Investigator questioning, or detected through laboratory test, or other means.

Adverse events include:

- Pre-existing medical conditions judged by the Investigator to have worsened in severity or frequency or changed in character during the protocol-specified AE reporting period (as specified in Section 9.4.1)
- Adverse events not previously observed in the subject that emerge during the protocol-specified AE reporting period (as specified in Section 9.4.1)
- Complications that occur as a result of protocol-mandated interventions
- Adverse events that occur prior to study treatment that are related to a protocol-mandated intervention (e.g., invasive procedures such as blood draws, sedation prior to IVT injection)

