When recording a death, the event or condition that caused or contributed to the fatal outcome should be recorded as a single medical concept. For example, if death resulted from respiratory failure, the AE recorded should be “Respiratory Failure”, and the outcome of the AE would be “Death”. If the cause of death is unknown and cannot be ascertained at the time of reporting, record “unexplained death” on the AE eCRF and SAE form.

e. Preexisting Medical Conditions

A preexisting medical condition is one that is present at the start of the study. Such conditions should be recorded on the Medical History eCRF.

A preexisting medical condition should be recorded as an AE or SAE only if the frequency, severity, or character of the condition worsens during the study. When recording such events on an AE eCRF and SAE form (if applicable), it is important to convey the concept that the preexisting condition has changed by including applicable descriptors (e.g., “more frequent headaches”).

f. Hospitalization, Prolonged Hospitalization or Surgery

Any AE that results in hospitalization or prolonged hospitalization should be documented and reported as an SAE unless specifically instructed otherwise in this protocol.

g. Pregnancy

If a female subject or a female partner of a male subject becomes pregnant during study participation of the female subject or the male partner, a Pregnancy Report form should be completed and faxed to the Sponsor within 24 hours of learning of the pregnancy, using the fax numbers listed in the Study Reference Manual.

Abortion, whether therapeutic or spontaneous, will also be reported on a Pregnancy Report form and faxed to the Sponsor. Refer to the Study Reference Manual for forms and complementary reporting information. If the abortion meets seriousness criteria (see Section 9.2.2, Serious Adverse Event Definition), this information will be captured on the AE eCRF and SAE form (if applicable).

Pregnancy should be followed up until after delivery, and any events to 3 months post-partum or termination of the pregnancy. Any congenital anomaly/birth defect in a child born to a female subject or to a female partner of a male subject exposed to the study drug should be recorded and reported as an SAE.

h. Special Situations Reporting

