10.9 Safety Analyses

10.9.1 Treatment Emergent Adverse Events

A treatment-emergent AE (TEAE) is defined as an event that was not present prior to administration of the first dose of study treatment and present after the first administration or if it represents the exacerbation of an event that was present prior to the first administration.

Adverse events noted during the study will be coded to system organ classes (SOCs) and preferred terms (PTs) using the Medical Dictionary for Regulatory Activities (MedDRA) dictionary. The overall incidence of TEAEs will be summarized by treatment group and classified by SOC and PT. Deaths, AE severity, serious AEs, relationship to study treatment and study discontinuation due to AE will also be tabulated by treatment group. An AE will be considered related to study treatment if the Investigator indicated the event is at least “possibly” related or if the relationship is missing. Adverse events with missing start dates, but with stop dates overlapping into the treatment period will be counted as treatment emergent. All AEs will be listed in subject listings and summarized by numbers and percentages of subjects by treatment group.

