#### **5.6.1. Partial and Missing Date/Time for Adverse Events**

Imputation of missing/partial AE date/time will be done only to identify TEAEs.

AE onset dates

- Partially missing onset date/time will be imputed as follows:
  - When only Day is missing:
    - If Month & Year of the onset date are the same as Month & Year of the first administration date, the imputed onset date will be imputed as the minimum of the first administration date/time and the AE resolution date (imputed if needed).
    - Otherwise, the missing day will be replaced by “1.”
  - When Day & Month are missing:
    - If Year of the onset date is the same as Year of the first administration date, the imputed onset date will be imputed as the minimum of the first administration date/time and the AE end date (imputed if needed).
    - Otherwise, the missing Day & Month will be replaced by “01 JAN.”
  - If a partial AE start date is consistent with the actual start date being on Day 1, and either the AE end date information is completely missing, or the complete or imputed AE end date/time information indicates that the AE did not end before Day 1, the imputed AE start date will be Day 1 in the following scenarios:
    - The AE start time is missing (the AE will be flagged as treatment-emergent following the first dose of study treatment)
    - The AE start time is after the date/time of first dosing of study treatment on Day 1 (the AE will be flagged as treatment-emergent following the first dose of study treatment)
    - The AE start time is before the time of first dosing of study treatment on Day 1, and imputing the AE start date as Day 2 instead of Day 1 would be inconsistent with the partially recorded AE start date (e.g., the calendar month for Day 2 is not the same as for Day 1), or with the complete or imputed AE end date/time (in this case, the AE will not be flagged as treatment-emergent following the first dose of study treatment).
  - Missing start time will be imputed with the time of administration if the day of AE start date and administration are identical, or with 00:00 otherwise.
- Completely missing onset dates for AEs will be imputed by the first administration date and the AE will be considered as treatment-emergent unless the end date/time of the AE (imputed if needed) or the end year of the AE (if day and month are missing) is entered

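### Protocol 9.4.1 classes AEs as treatment-emergent by when they are noted, against the protocol's and SAP's onset-based rules, so imprecisely dated pre-existing conditions can reach the TEAE tables

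*Protocol*

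**What the plan says.** Protocol 9.4.1 (Adverse Event Reporting Period) has three capture rules:

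- Medical history: "known pre-existing medical conditions found during the screening period and up to initiation of dosing will be captured as medical history".
- Pre-dose events: an event not already part of medical history and "occurring before first dose of study treatment will be captured as a non-treatment emergent AE".
- Post-dose events: "Any event/condition noted once the subject receives their dose of study drug will be captured as a treatment emergent AE".

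Other sections treat a pre-existing condition differently:

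- Protocol 9.2.1, among the things that count as AEs, lists "Pre-existing medical conditions judged by the Investigator to have worsened in severity or frequency or changed in character".
- Protocol 9.4.3, item e, assigns conditions present when the study starts to the Medical History eCRF, whenever they are found. Such a condition "should be recorded as an AE or SAE only if the frequency, severity, or character of the condition worsens during the study".
- Protocol 10.9.1 describes a TEAE as "defined as an event that was not present prior to administration of the first dose of study treatment and present after the first administration", or as the exacerbation of something already there. SAP 5.6 uses the same idea and names the sham procedure explicitly.
- SAP 5.6.1 derives the TEAE flag from the onset date, imputed where necessary: "Completely missing onset dates for AEs will be imputed by the first administration date and the AE will be considered as treatment-emergent", unless the event ended before that date.

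**The concern.** The post-dose rule in 9.4.1 turns on when a condition is noted. The neighbouring rules turn on when it began or whether it changed. For a condition that predates dosing, has not changed and is first seen at a later examination, a site cannot follow both 9.4.1 and 9.4.3e. Different sites may resolve the conflict differently.

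The situation is plausible in this trial. Subjects have progressive retinal disease, cystoid macular edema is allowed at entry if stable, and both eyes are examined repeatedly.

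What is at stake is the meaning of the AE output. SAP section 6 drops all formal analysis and keeps tables only for disposition, demographic and baseline characteristics, and an overview of AEs. AE summaries are therefore among the few analyses left, and the capture rule feeds them.

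**Working it through.** No sample size, power or event count is at issue, so the check is a trace of one test case through each rule. The case is a condition that began before the first dose, was first noted after it, and did not worsen.

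**Step 1: site recording rules**

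| Rule | What it tests | Result for the test case |
|---|---|---|
| 9.4.1, post-dose sentence | when noted | captured as a TEAE |
| 9.4.1, medical-history sentence | when found | no route to medical history, because found after dosing |
| 9.4.1, pre-dose sentence | when it occurred | if it began between consent and dosing, an AE that is not treatment-emergent |
| 9.2.1 | worsening or change in character | not an AE |
| 9.4.3e | presence at study start; worsening | Medical History eCRF; not an AE |

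Section 9.4.1 conflicts with 9.2.1 and 9.4.3e. For a condition arising between consent and dosing it also conflicts with itself.

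**Step 2: analysis definitions**

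Under Protocol 10.9.1 and SAP 5.6 the test case is not a TEAE, since it was present before dosing and did not worsen.

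**Step 3: the flag as SAP 5.6.1 would derive it**

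Suppose the site follows 9.4.1 and enters the condition as an AE. The flag then depends on what is recorded:

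1. Complete onset date before dosing: not flagged.
2. Day missing, in a month before the first-dose month: set to the first of that month, hence before dosing; not flagged.
3. Day and month missing, in a year before the first-dose year: set to 1 January of that year; not flagged.
4. End date before dosing: not flagged, even with onset missing.
5. Day missing in the first-dose month, or day and month missing in the first-dose year, with no pre-dose end: generally set to first administration and flagged.
6. Onset wholly missing, with no pre-dose end: set to first administration and flagged. Protocol 10.9.1 points the same way when the stop date overlaps treatment.
7. Date noted entered as the onset date: a complete post-dose date, so flagged. No SAP rule can detect this.

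Only cases 5, 6 and 7 put the condition into the TEAE counts.

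**Step 4: which outputs are touched**

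- AE listings: SAP 5.3.1 reports listings as entered on the eCRF, so all seven cases would be listed.
- TEAE tables: cases 5 to 7 only. The SOC and preferred-term TEAE tables named in SAP 5.6 are ocular, for the treated and the contralateral eye.
- Overview tables: their titles refer to AEs, not TEAEs. Whether they are restricted to TEAEs depends on output shells held in a separate document.

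**Step 5: size**

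The documents give neither a rate of late-noted pre-existing conditions nor a rate of missing or partial onset dates, so the effect cannot be computed. As a unit of scale only, at the planned 27 per arm one wrongly flagged subject adds at most 1/27 = 3.7 percentage points to one row in that arm. The study stopped early and the actual denominators are not given.

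**The case against.** The strongest reply is that 9.4.1 is an instruction to sites and does not define the tabulated TEAEs. Those are set by 10.9.1, SAP 5.6 and SAP 5.6.1, which look at prior presence and onset. This stands. A reader might infer from 9.4.1 that late-noted pre-existing conditions enter the TEAE counts as a matter of course. The documents do not support that, because cases 1 to 4 above are screened out.

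Further points for the plan:

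- A site that reads 9.2.1 and 9.4.3e has a specific rule for this case, and the eCRF completion guidelines, which are not available here, may repeat it. This softens the problem but leaves two current sections in contradiction.
- Screening examines both eyes and must be completed in full, so most existing ocular findings should be known before Day 1. That is fair, and nothing in the documents shows that onset is usually unknown for the remainder.
- Treating missing onsets as treatment-emergent is a conservative safety default, stated in both documents. That stands, and SAP 5.6.1 needs no change.
- Section 9.4.1 refers to study drug, which sections 6.1.5 and 10.3 distinguish from sham. Read literally, this would leave sham subjects without a starting point for TEAE capture. SAP 5.6 and 10.9.1 cover sham where counts are made, so this is a wording fault only.

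A reader might also infer a bias between arms: dilution if such findings fall evenly, or inflation in injected eyes if section 4.2.1.3 leads to more examinations there. Both are conjecture. The documents provide for no formal comparison and give no data on examination frequency by arm.

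**Conclusion.** The contradiction is confirmed on the text. Section 9.4.1 classifies by when a condition is noted, and cannot be reconciled with 9.2.1, 9.4.3e, 10.9.1 or SAP 5.6 for an unchanged pre-existing condition first noted after dosing. Such a condition can reach the AE eCRF and listings, and the TEAE tables in three situations: wholly missing onset, partial onset in the first-dose month or year (each without a pre-dose end), or the date noted entered as onset.

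This assumes that at least some sites follow 9.4.1 rather than 9.4.3e. Size and direction are unknown. Since the remaining output is descriptive and the analysis definitions screen out most dated records, severity is minor.

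**What to change.** Reword the post-dose sentence of 9.4.1 along these lines:

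*An event with onset after the first administration of study treatment (ultevursen or sham-procedure), or a worsening of a pre-existing condition after that time, is captured as treatment-emergent. A condition first noted after dosing that the masked Investigator judges to have been present before Day 1, and not to have worsened, is entered on the Medical History eCRF. See 9.4.3e and 10.9.1.*

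Bring the eCRF completion guidelines into line if they follow the present sentence.

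Rewording does little for data already collected. For close-out, query AE entries with missing or partial onset before database lock, and ask whether the condition predated Day 1 and whether it changed. This will not find entries where the date noted was used as onset. Adding entries whose onset date coincides with an examination visit would help with those.

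The cost is a short text change and a limited set of queries. The one drawback is that the masked Investigator must judge whether a late-noted finding was already present.

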9.4.2 Eliciting Adverse Events

A consistent methodology of non-directive questioning for eliciting AEs at all subject evaluation time points should be adopted. Examples of non-directive questions include:

“How have you felt since your last clinic visit?”

“Have you had any new or changed health problems since you were last here?”

9.4.3 Recording Adverse Events and Serious Adverse Events

Investigators should use correct medical terminology/concepts when recording AEs or SAEs on the eCRF and/or AESI/SAE/Special Situation reporting form. Colloquialisms and abbreviations should be avoided. Serious AEs must also be recorded on the AE eCRF or AESI/SAE/Special Situation reporting form. Only 1 medical concept should be recorded in the event field on the AE eCRF and AESI/SAE/Special Situation reporting form (if applicable).

a. Adverse Events Occurring Secondary to Other Events

In general, AEs occurring secondary to other events (e.g., cascade events or clinical sequelae) should also be entered as separate AEs. For example, if severe diarrhea is known to have resulted in dehydration, both diarrhea and dehydration should be entered as AEs on the eCRF, and if also serious, as SAE on AE eCRF and AESI/SAE/Special Situation reporting form (if applicable).

b Persistent or Recurrent Adverse Events

A persistent AE is one that extends continuously, without resolution between subject evaluation time points. Such events should only be recorded once in the eCRF unless their severity increases. If a persistent AE becomes more severe or occurs more frequently, it should be recorded again on the AE eCRF with the increased severity grading.

A recurrent AE is one that occurs and resolves between subject evaluation time points and subsequently recurs. All recurrent AEs should be recorded individually on the AE eCRF.

c. Abnormal Laboratory Values

Only clinically significant laboratory abnormalities will be recorded as AEs on the eCRF and SAE form (if applicable).

If the laboratory abnormality can be characterized by a precise clinical term, the clinical term should be recorded as the AE or SAE. For example, an elevated serum potassium level of 7.0 mEq/L should be recorded as “hyperkalemia”.

Observations of the same clinically significant laboratory abnormality from visit to visit should not be repeatedly recorded as AEs on the eCRF and SAE form (if applicable), unless their severity, seriousness, or etiology changes.

d. Deaths

All deaths that occur during the protocol-specified AE reporting period (see Section 9.4.1), regardless of attribution, will be recorded on the AE eCRF and SAE form and reported to the Sponsor within 24 hours of event knowledge.

When recording a death, the event or condition that caused or contributed to the fatal outcome should be recorded as a single medical concept. For example, if death resulted from respiratory failure, the AE recorded should be “Respiratory Failure”, and the outcome of the AE would be “Death”. If the cause of death is unknown and cannot be ascertained at the time of reporting, record “unexplained death” on the AE eCRF and SAE form.

e. Preexisting Medical Conditions

A preexisting medical condition is one that is present at the start of the study. Such conditions should be recorded on the Medical History eCRF.

A preexisting medical condition should be recorded as an AE or SAE only if the frequency, severity, or character of the condition worsens during the study. When recording such events on an AE eCRF and SAE form (if applicable), it is important to convey the concept that the preexisting condition has changed by including applicable descriptors (e.g., “more frequent headaches”).

f. Hospitalization, Prolonged Hospitalization or Surgery

Any AE that results in hospitalization or prolonged hospitalization should be documented and reported as an SAE unless specifically instructed otherwise in this protocol.

g. Pregnancy

If a female subject or a female partner of a male subject becomes pregnant during study participation of the female subject or the male partner, a Pregnancy Report form should be completed and faxed to the Sponsor within 24 hours of learning of the pregnancy, using the fax numbers listed in the Study Reference Manual.

Abortion, whether therapeutic or spontaneous, will also be reported on a Pregnancy Report form and faxed to the Sponsor. Refer to the Study Reference Manual for forms and complementary reporting information. If the abortion meets seriousness criteria (see Section 9.2.2, Serious Adverse Event Definition), this information will be captured on the AE eCRF and SAE form (if applicable).

Pregnancy should be followed up until after delivery, and any events to 3 months post-partum or termination of the pregnancy. Any congenital anomaly/birth defect in a child born to a female subject or to a female partner of a male subject exposed to the study drug should be recorded and reported as an SAE.

h. Special Situations Reporting

Medication errors and uses outside what is foreseen in the protocol, including overdose and occupational exposure must be reported to the Sponsor within 24 hours from awareness on an paper AESI/SAE/Special Situation reporting form (if applicable) for tracking purposes and will be considered a protocol deviation. Overdose is defined as any study drug dose administered above the intended dose for the cohort assignment. Additional instructions for reporting special situation information will be provided by the Sponsor at the time of notification.

